##### 4.1.1 Subjects Using Any Hormonal Birth Control Method

Subjects using any hormonal birth control method can have LevoCept placed on any day of the menstrual cycle. If the insertion occurs in the first 7 days of the cycle, the hormonal contraception can be discontinued after insertion. If the insertion occurs after the first 7 days of the menstrual cycle, the subject should continue using hormonal contraception for an additional 7 days.

- Subjects using an implant (Implanon/Nexplanon) who have regular cycles, LevoCept should be inserted within seven days of onset of menses and the implant may be removed the same day.
- Subjects using an implant (Implanon/Nexplanon) who have irregular cycles or amenorrhea, LevoCept should be inserted and the implant should be removed seven days after IUD inserted
- Subjects using an implant (Implanon/Nexplanon) with regular cycles but who are beyond seven days of menses, LevoCept may be inserted but removal of implant should occur after seven days.

- Subjects using levonorgestrel IUD can have IUD removed and LevoCept placed on the same day. Insertion can occur on any day of the cycle.

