## **20.5 Pre-Trial and Concomitant Medications**

Concomitant medications include any medication or health product (any prescription medications or over-the-counter preparations) taken during the study. Pre-trial medications include any contraception or medication used to treat a prior cervical infection taken within 30 days of screening. The number and percentage of subjects using medications, as captured on the Concomitant Medication eCRF, will be tabulated according to the medication's World Health Organization Anatomical Therapeutic Drug Class and Generic Term. Pre-trial and concomitant medications will be presented separately.

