6.1 General Methodology

Analyses will be implemented using SAS® 9.4 or above. In general, all efficacy and safety variables will be summarised using descriptive statistics and graphs as appropriate. Continuous variables will be summarised by descriptive statistics (sample size (n), mean, standard deviation (SD), minimum, median, and maximum). Categorical variables will be summarised in frequency tables (frequencies and percentages). Time to event variables will be summarised by Kaplan-Meier estimates of median and quartile time to events. Individual data will be presented in subject listings.

Means and medians will be displayed with one more decimal place than the collected data, and SDs will have one more decimal place than the means and medians. Minimum and maximum will be displayed with the same number of decimal places as the collected data. Percentages will be rounded to one decimal place.

No formal statistical testing will be performed on subject disposition, demographic, baseline characteristic, and safety data. Where appropriate, point estimates, together with their 95% confidence intervals will be presented.

Only observed data, with no data imputation, will be used for the efficacy analyses unless otherwise specified. Safety analyses will also be conducted on the observed data. However, for the start date/time of an AE or medication being partially or completely missing, the worst case scenario will be applied. That is, the AE will be assumed to be treatment emergent, and the medication will be considered to be concomitant.

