Missing	Known	If stop date < study med start date, then not TEAE; If stop date ≥ study med start date, then TEAE.
	Partial	Impute stop date as latest possible date (i.e. last day of month if day is unknown or 31 December if day and month are unknown), then: If stop date < study med start date, then not TEAE; If stop date ≥ study med start date, then TEAE.
	Missing	Assumed TEAE

CONFIDENTIAL

Algorithm for Prior/Concomitant Medications:

Start Date	Stop Date	Action
Known	Known/Partial/Missing	If start date < study med start date, then assign as prior; If start date \geq study med start date, then assign as concomitant.
Partial	Known/Partial/Missing	Impute start date as earliest possible date (i.e. first day of month if day is unknown or 1st January if day and month are unknown), then: If start date < study med start date, then assign as prior; If start date \geq study med start date, then assign as concomitant.
Missing	Known	If stop date < study med start date, then assign as prior; If stop date \geq study med start date, then assign as concomitant.
	Partial	Impute stop date as latest possible date (i.e. last day of month if day is unknown or 31 December if day and month are unknown), then: If stop date < study med start date, then assign as prior; If stop date \geq study med start date, then assign as concomitant.
	Missing	Assign as concomitant

12 Appendix 2 List of Tables, Figures, and Listings

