14.1.11.3 Both Prior and Concomitant Medication (All Enrolled Subjects)

Update the cell at first column first row to 'Patients with both prior and Concomitant Medications'.

CONFIDENTIAL

Sebela Pharmaceuticals Development LLC
CMDOC-0022

Page x of y

Table 14.2.1
Pearl Index (EP Population)

	Number of Subjects	Number of Pregnancies	Number of Woman-Cycles at Risk	Pearl Index	95% CI for Pearl Index
1-Year					
All EP Subjects	n	n	n	x.xx	x.xx, x.xx
EP Subjects by Parity					
Parous	n	n	n	x.xx	x.xx, x.xx
Nulliparous	n	n	n	x.xx	x.xx, x.xx
EP Subjects by BMI					
Underweight (<18.5)	n	n	n	x.xx	x.xx, x.xx
Normal (18.5-24.9)	n	n	n	x.xx	x.xx, x.xx
Overweight (25.0-29.9)	n	n	n	x.xx	x.xx, x.xx
Obese (>=30)	n	n	n	x.xx	x.xx, x.xx
2-Year					
All EP Subjects	n	n	n	x.xx	x.xx, x.xx
EP Subjects by Parity					
Parous	n	n	n	x.xx	x.xx, x.xx
Nulliparous	n	n	n	x.xx	x.xx, x.xx
EP Subjects by BMI					
Underweight (<18.5)	n	n	n	x.xx	x.xx, x.xx
Normal (18.5-24.9)	n	n	n	x.xx	x.xx, x.xx
Overweight (25.0-29.9)	n	n	n	x.xx	x.xx, x.xx
Obese (>=30)	n	n	n	x.xx	x.xx, x.xx
Cumulative 2-Year					
.....					
3-Year					
.....					
Cumulative					

EP=Evaluable for Pregnancy.

Reference: Listing xxx.

Program Location: \\xx\xxx\xxx\xxx\xxxxxx\xxxxxxxxxxxxxxxxxxxx\xxxx\xxxxx.sas

date

time

Programmer note:

1.Table will continue with for Cumulative 2-Year, 3-Year,Cumulative

CONFIDENTIAL

Sebela Pharmaceuticals Development LLC
CMDOC-0022

Page x of y

Table 14.2.2
Pregnancy Rate (EP Population)

	Parous (N=xx)	Nulliparous (N=xx)	All Subjects (N=xx)
Number of Subjects with Pregnancy	n (%)	n (%)	n (%)
Number of subjects who was not Pregnant(Censored)	n (%)	n (%)	n (%)
Pregnancy Free (Days)			
Pregnancy Rate[1]			
1-Year	xx	xx	xx
2-Year	xx	xx	xx
Cumulative 2-Year	xx	xx	xx
3-Year	xx	xx	xx
Cumulative	xx	xx	xx
Range (Subjectswith Pregnancy)	xx -xx	xx -xx	xx -xx
Range (All Subjects)	xx -xx	xx -xx	xx -xx

[1] Kaplan-Meier product-limit estimates.

Reference: Listing xxx.

Program Location: \\xx\xxx\xxx\xxx\xxxxxx\xxxxxxxxxxxxxxxx\xxxx\xxxxx.sas

date

time

CONFIDENTIAL

Sebela Pharmaceuticals Development LLC
CMDOC-0022

Page x of y

Table 14.3.1.1.1
Overall Summary of Treatment-Emergent Adverse Events (Safety Population)

	Events (N=xx) n	Subjects (N=xx) n (%)
Onset Time Frame:		
Missing	n	n (%)
From Day 1 through Day 42(Week 6)	n	n (%)
From Day 43 through Day 91(Week 13)	n	n (%)
From Day 92 through Day 182(Week 26)	n	n (%)
From Day 183 through Day 364(Week 52)	n	n (%)

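### SAP Appendix 1 classes medication that starts before placement and continues afterwards as prior and not concomitant, against protocol 20.5 and the SAP's own table and listing shells

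*SAP*

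**What the plan says.** SAP Appendix 1, Algorithm for Prior/Concomitant Medications, has three kinds of row.

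- **Known start date**, with the stop date known, partial or missing: "If start date < study med start date, then assign as prior"; otherwise concomitant.
- **Partial start date**, with the same three stop-date states: "Impute start date as earliest possible date (i.e. first day of month if day is unknown or 1st January if day and month are unknown", followed by the same test.
- **Missing start date**: here the stop date decides. "If stop date < study med start date, then assign as prior"; if the stop date is on or after placement, or missing, the drug is concomitant.

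Four other places bear on this.

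- Protocol 20.5: "Concomitant medications include any medication or health product (any prescription medications or over-the-counter preparations) taken during the study". It defines pre-trial medication narrowly: "Pre-trial medications include any contraception or medication used to treat a prior cervical infection taken within 30 days of screening".
- SAP 6.1: where a medication's start date is partly or wholly missing, the worst case applies and "the medication will be considered to be concomitant".
- The SAP outputs: Table 14.1.11.3 is titled "Both Prior and Concomitant Medication (All Enrolled Subjects". Listing 16.2.4.6 has separate Prior and Concomitant columns, and one mock record shows Yes in both.
- Protocol 4.1.1: when insertion falls after the first 7 days of the cycle, "the subject should continue using hormonal contraception for an additional 7 days".

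**The concern.** A concomitant medication table is meant to show what subjects were taking while they had the device. Two of the three kinds of row in Appendix 1 never look at the stop date, so long-term treatment begun before placement drops out of that table. Hormonal contraception that protocol 4.1.1 directs some subjects to continue after insertion drops out as well, where it is recorded as medication. A reader of Table 14.1.11.2 who is interpreting adverse events or bleeding would see an incomplete picture of drug use.

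The partial-date row raises a second, separate problem. Two parts of the SAP give different answers for the same record, and Appendix 1 takes the less cautious one.

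**Working it through.** The plan states no figure on this point, so there is none to reproduce. The check applies the Appendix 1 rows to a set of date patterns and compares the results with the other passages.

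Assumptions: the appendix's reference date is the date of successful placement (Day 1), set here to 15 May 2017. That date is arbitrary; only the order of dates matters.

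| # | Start | Stop | Appendix 1 as written | With the fix below |
|---|---|---|---|---|
| 1 | 1 Jan 2016 | ongoing | prior | prior + concomitant |
| 2 | 1 Jan 2016 (hormonal contraceptive) | 22 May 2017 (Day 8) | prior | prior + concomitant |
| 3 | 1 Jan 2016 | 1 May 2017 | prior | prior |
| 4 | 20 May 2017 | ongoing | concomitant | concomitant |
| 5 | 2015 (set to 1 Jan 2015) | ongoing | prior | prior + concomitant |
| 6 | May 2017 (set to 1 May 2017) | ongoing | prior | concomitant |
| 7 | 2017 (set to 1 Jan 2017) | ongoing | prior | concomitant |
| 8 | missing | ongoing | concomitant | concomitant |
| 9 | missing | 1 Jun 2017 | concomitant | concomitant |
| 10 | missing | 1 May 2017 | prior | prior |

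**Continuing drugs.** In patterns 1, 2 and 5 the drug certainly began before placement and was certainly used after it. Protocol 20.5 makes each of them concomitant; Appendix 1 does not. Patterns 1 and 8 show the anomaly most clearly: an ongoing drug counts as concomitant if its start date is missing, but not if its start date is known and earlier.

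**The both category.** Each row of the algorithm assigns one class, and none of the ten patterns returns both. The record flagged Yes/Yes in Listing 16.2.4.6 cannot arise from this algorithm.

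**Partial start dates.** In patterns 6 and 7 the drug may have started after placement. Earliest-date imputation gives prior; SAP 6.1 gives concomitant. The adverse event algorithm in the same appendix treats this situation differently: it has a branch for partial dates that could fall on or after the reference date, and lets the stop date decide. The medication algorithm has no such branch.

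**Tally.** Three patterns gain a concomitant flag under the fix (1, 2, 5), two move from prior to concomitant (6, 7) and five do not change: 3 + 2 + 5 = 10. These counts describe the test set and do not estimate how many study records are affected.

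**The case against.** The strongest case on the other side is that the SAP plainly intends a both category, that nothing is lost from the report, and that these are frequency tables with no inference. Much of this stands, and it limits the point. Several stronger readings that a reader might infer are not supported.

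- *Every drug begun before placement is misclassified.* No. With a missing start date the stop date decides, and a continuing drug becomes concomitant (patterns 8 and 9).
- *Continuing drugs vanish from the report.* No. They stay in Table 14.1.11.1 and in Listing 16.2.4.6, which shows start and stop dates or ongoing status.
- *At-risk cycles or the Pearl Index are affected.* No. SAP 4.1 excludes cycles on back-up or emergency contraception reported by the subject. The e-diary captures additional contraception, including hormonal methods, and the missed-diary review and monthly contact also ask about it. No rule shown uses the prior/concomitant class to exclude a cycle.
- *Table 14.1.11.3 must be empty.* This holds only at the level of the single drug record. Its first-row label can be read as counting subjects who have at least one drug of each class. That reading would fill the table, but it would not bring an ongoing drug into the concomitant class.
- *The SAP nowhere defines both.* This cannot be asserted. The SAP text available for this review goes from section 6.2.6 to 6.2.9, so a medication section may exist that was not seen.

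One might also argue that protocol 20.5 asks for the two classes to be presented separately, so one class per record was meant. Separate tables do not require exclusive classes, and the Yes/Yes record shows that the SAP did not intend them to be exclusive.

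None of this removes the conflict between the Appendix 1 rows and protocol 20.5, the shells and SAP 6.1.

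**Conclusion.** The point holds, within limits. For known start dates, and for partial dates imputed before placement, Appendix 1 ignores the stop date. It contradicts protocol 20.5 and cannot produce the both records that the SAP's own listing displays. This is a wrong rule rather than a missing detail: followed literally, it leaves continuing medication out of Table 14.1.11.2. The conflict with SAP 6.1 over partial start dates is a second, independent defect. SAP 8.2 lists two changes from the protocol's analyses, and neither concerns medication.

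The consequence is confined to descriptive medication tables. The primary analysis is untouched. The number of affected records or subjects cannot be computed, because the documents give no medication data.

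The conclusion assumes that the reference date in the appendix means placement, and that no section unseen here overrides the appendix. If such a section exists, the two texts still have to be reconciled.

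**What to change.** Replace the single-class algorithm with two independent flags.

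- **Prior:** start date before Day 1, including a partial date whose known components place it before Day 1. A record whose stop date is before Day 1 is also prior, so that no record is left without a flag.
- **Concomitant:** start date on or after Day 1; or stop date on or after Day 1, ongoing or missing. Impute a partial stop date to the latest possible date.
- **Partial or missing start that could fall on or after Day 1:** flag concomitant unless the stop date is before Day 1. This follows the worst-case intent of SAP 6.1. Since SAP 6.1 does not mention the stop date, add that exception there so that the two texts give one rule.

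A drug with start year 2015 that is still taken then keeps its prior flag and gains the concomitant one.

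State that records with both flags are counted in Table 14.1.11.2 as well as Table 14.1.11.3, and whether the latter counts drug records or subjects.

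Reconcile the Day 1 split with the protocol. Sections 4.6 and 14 count concomitant use from consent to study exit, and 20.5 limits pre-trial medication to two drug groups within 30 days of screening. A drug started and stopped between consent and placement is concomitant under 4.6 and 14 but prior under a Day 1 split. Either align the definitions or list the difference in SAP 8.2. Check any medication section between SAP 6.2.6 and 6.2.9 against the new wording.

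The cost is an appendix edit, a sentence or two in SAP 6.1 and possibly 8.2, and a small programming change. No new data are needed.

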12.1 Index of Tables

CONFIDENTIAL

ICH Heading	Table Number	Table Description
14.1		Demographics
	14.1.1	Subject Disposition (All Screened Subjects)
	14.1.2	Disposition by Site (All Enrolled Subjects)
	14.1.3	Summary of Subjects at Each Scheduled Study Visit (All Enrolled Subjects)
	14.1.4	Summary of Subjects with Protocol Deviations (All Enrolled Subjects)
	14.1.5	Analysis Populations (All Enrolled Subjects)
	14.1.6	Demographics and Baseline Characteristics (All Enrolled Subjects)
	14.1.7	Medical History (All Enrolled Subjects)
	14.1.8	Gynecological History (All Enrolled Subjects)
	14.1.9	Menstrual History (All Enrolled Subjects)
	14.1.10	Cervical Cytology (All Enrolled Subjects)
	14.1.11.1	Prior Medication (All Enrolled Subjects)
	14.1.11.2	Concomitant Medication (All Enrolled Subjects)
	14.1.11.3	Both Prior and Concomitant Medication (All Enrolled Subjects)
14.2		Efficacy
	14.2.1	Pearl Index (EP Population)
	14.2.2	Pregnancy Rate (EP Population)
14.3		Safety
14.3.1		Displays of Adverse Event
	14.3.1.1.1	Overall Summary of Treatment-Emergent Adverse Events (Safety Population)
	14.3.1.1.2	Overall Summary of Adverse Events (All Enrolled Subjects)
	14.3.1.2.1	Overall Summary of Treatment-Emergent Adverse Events by Severity and Relatedness to the Study Product (Safety Population)
	14.3.1.2.2	Overall Summary of Adverse Events by Severity and Relatedness to the Study Product (All Enrolled Subjects)
	14.3.1.3.1	Treatment-Emergent Adverse Events by System Organ Class and Preferred Term (Safety Population)
	14.3.1.3.2	Adverse Events by System Organ Class and Preferred Term (All Enrolled Subjects)
	14.3.1.4.1	Treatment-Emergent Serious Adverse Events by System Organ Class and Preferred Term (Safety Population)
	14.3.1.4.2	Serious Adverse Events by System Organ Class and Preferred Term (All Enrolled Subjects)
	14.3.1.5	Treatment-Emergent Adverse Events Leading to Study Device Removal (Safety Population)
	14.3.1.6	Treatment-Emergent Adverse Events as Primary Reason for Exiting Study (Safety Population)
	14.3.1.7	Treatment-Emergent Adverse Events Leading to Death (Safety Population)
	14.3.1.8	Treatment-Emergent Adverse Events by System Organ Class, Preferred Term and Severity (Safety Population)
	14.3.1.9	Treatment-Emergent Adverse Events by System Organ Class, Preferred Term and Relatedness to Study Device (Safety Population)
	14.3.1.10	Treatment-Emergent Adverse Events by System Organ Class and Preferred Term and by Relatedness to Study Device Placement/Removal Procedure (Safety Population)
	14.3.1.11	Treatment-Emergent Adverse Events by Preferred Term (Safety Population)
	14.3.1.12	Treatment-Emergent Adverse Events by Preferred Term by Onset Time Frame for the First Year (Safety Population)
	14.3.1.13	Treatment-Emergent Adverse Events by Preferred Term by Onset Time Frame (Safety Population)
14.3.2		Listings of Deaths, Other Serious and Significant Adverse Events
	14.3.2.1	Deaths (All Enrolled Subjects)

CONFIDENTIAL

ICH Heading	Table Number	Table Description
	14.3.2.2	Serious Adverse Events (All Enrolled Subjects)
	14.3.2.3	Adverse Events as Primary Reason for Exiting Study (All Enrolled Subjects)
14.3.5		Exposure
	14.3.5.1	Treatment Exposure (All Enrolled Subjects)
	14.3.5.2	Device Placement and Subject Pain During the Procedure (All Enrolled Subjects)
	14.3.5.3	Device Expulsion/Removal and Subject Pain During the Procedure (Safety Population)
	14.3.5.4	Transvaginal Ultrasound (Safety Population)
14.3.6		Individual Patient-Reported Outcome Measurements
	14.3.6.1.1	Bleeding and Spotting by Cycle (Safety Population)
	14.3.6.1.2	Bleeding and Spotting by Cycle (ECYC Population)
	14.3.6.2.1	Occurrence and Severity of Dyspareunia in Number of Days by Cycle (Safety Population)
	14.3.6.2.2	Occurrence and Severity of Dyspareunia in Number of Days by Cycle (ECYC Population)
	14.3.6.2.3	Occurrence and Severity of Dyspareunia – Worst Pain Grade Shift from Baseline by Cycle (Safety Population)
	14.3.6.2.4	Occurrence and Severity of Dyspareunia – Worst Pain Grade Shift from Baseline by Cycle (ECYC Subjects)
	14.3.6.2.5	Occurrence and Severity of Dyspareunia – Highest Frequency of Occurrence Pain Grade Shift from Baseline by Cycle (Safety Population)
	14.3.6.2.6	Occurrence and Severity of Dyspareunia – Highest Frequency of Occurrence Pain Grade Shift from Baseline by Cycle (ECYC Subjects)
	14.3.6.3.1	Occurrence and Severity of Menstrual Pain or Cramping in Number of Days by Cycle (Safety Population)
	14.3.6.3.2	Occurrence and Severity of Menstrual Pain or Cramping in Number of Days by Cycle (ECYC Population)
	14.3.6.3.3	Occurrence and Severity of Menstrual Pain or Cramping by Cycle (Safety Population)
	14.3.6.3.4	Occurrence and Severity of Menstrual Pain or Cramping by Cycle (ECYC Population)
14.3.7		Vital Signs and Other Data
	14.3.7.1	Vital Signs and Weight by Analysis Visit (Safety Subjects)
	14.3.7.2	BMI Category by Analysis Visit (Safety Subjects)

12.2 Index of Figures

Figure Number	Figure Description
14.2.1.1	Kaplan-Meier Plot of Time in days to pregnancy (EP Population)
14.2.1.2	Kaplan-Meier Plot of Time in days to pregnancy up to 1 year (EP Population)
14.2.1.3	Kaplan-Meier Plot of Time in days to pregnancy up to 2 years (EP Population)

12.3 Index of Listings

CONFIDENTIAL

ICH Heading	Listing Number	Listing Description
16.2		Subject DATA LISTINGS
16.2.1		Discontinued Subjects
	16.2.1.1	Subject Disposition (All Screened Subjects)
	16.2.1.2	Subjects Who Prematurely Discontinued the 1-Year Study (All Enrolled Subjects)
	16.2.1.3	Subjects Who Prematurely Discontinued the Extension Study (Extension Population)
	16.2.1.4	Study Exit Status (All Screened Subjects)
16.2.2		Protocol Deviations
	16.2.2.1	Eligibility (All Screened Subjects)
	16.2.2.2	Protocol Deviations (All Screened Subjects)
16.2.3		Subjects Excluded from the Efficacy Analysis
	16.2.3.1	Subject Status on Analysis Population (All Screened Subjects)
16.2.4		Demographics and Baseline Characteristics
	16.2.4.1	Demographics (All Enrolled Subjects)
	16.2.4.2	Medical History (All Enrolled Subjects)
	16.2.4.3	Gynecological History (All Enrolled Subjects)
	16.2.4.4	Menstrual History (All Enrolled Subjects)
	16.2.4.5	Cervical Cytology (All Enrolled Subjects)
	16.2.4.6	Prior and Concomitant Medications (All Enrolled Subjects)
16.2.5		Study Drug Exposure
	16.2.5.1	Device Placement (All Enrolled Subjects)
	16.2.5.2	Device Removal (All Enrolled Subjects)
	16.2.5.3	Transvaginal Ultrasound (All Enrolled Subjects)
16.2.6		Individual Efficacy Response Data
	16.2.6.1	Pregnancy Test (All Enrolled Subjects)
	16.2.6.2	Post-Expulsion Pregnancy Test (All Enrolled Subjects)
	16.2.6.3	Post-Removal Pregnancy Test (All Enrolled Subjects)
	16.2.6.4	Pregnancy Notification (All Enrolled Subjects)
	16.2.6.5	Pregnancy Outcome (All Enrolled Subjects)
	16.2.6.6	Return to Fertility (All Enrolled Subjects)
16.2.7		Adverse Event Listings
	16.2.7.1	Adverse Events (All Enrolled Subjects)
	16.2.7.2	Adverse Events Related to Study Device (All Enrolled Subjects)
	16.2.7.3	Adverse Events Related to Study Device Placement/Removal Procedure (All Enrolled Subjects)
	16.2.7.4	Adverse Events Leading to Study Device Removal (All Enrolled Subjects)
	16.2.7.5	Adverse Events Leading to Death (All Enrolled Subjects)
16.2.8		Individual Patient-Reported Outcome Measurements
	16.2.8.1	Subject Diary (All Enrolled Subjects)
	16.2.8.2	Subject Missed Diary Review (All Enrolled Subjects)
	16.2.8.3	Monthly Phone Contact (All Enrolled Subjects)

CONFIDENTIAL

ICH Heading	Listing Number	Listing Description
	16.2.8.4	Subject Study Visits (All Enrolled Subjects)
	16.2.8.5	Long Term Follow-up (Extension Population)
16.2.9		Vital Signs and Other Data
	16.2.9.1	Height (All Enrolled Subjects)
	16.2.9.2	Vital Signs (All Enrolled Subjects)
	16.2.9.3	Vital Signs – Change from Baseline Results (All Enrolled Subjects)
	16.2.9.4	Physical Examination (All Enrolled Subjects)
	16.2.9.5	Pelvic Examination (All Enrolled Subjects)

13 Appendix 3 Table Layouts

CONFIDENTIAL

Sebela Pharmaceuticals Development LLC
CMDOC-0022

Page x of y

Table 14.1.1
Subject Disposition (All Screened Subjects)

Description	Enrolled [1] (N=xx) n (%)	All Subjects (N=xx) n (%)
Screen Failure		n (%)
Safety Population [2]	n (%)	n (%)
Discontinued 1-Year Study Prematurely	n (%)	n (%)
Completed 1-Year Study	n (%)	n (%)
Entered the Extension Study	n (%)	n (%)
Discontinued Extension Study Prematurely	n (%)	n (%)
Completed Extension Study	n (%)	n (%)
Reason for Discontinuation of 1-Year Study		
Adverse Event	n (%)	n (%)
Withdrew Consent	n (%)	n (%)
Protocol Violation	n (%)	n (%)
Lost to Follow-up	n (%)	n (%)
Investigator/Sponsor Decision	n (%)	n (%)
Pregnancy	n (%)	n (%)
Other	n (%)	n (%)
Screen Failure [3]		n (%)
Reason for Discontinuation of Extension Study		
Adverse Event	n (%)	n (%)
Withdrew Consent	n (%)	n (%)
Protocol Violation	n (%)	n (%)
Lost to Follow-up	n (%)	n (%)
Investigator/Sponsor Decision	n (%)	n (%)
Pregnancy	n (%)	n (%)
Other	n (%)	n (%)

Note: Percentages are based on the number of subjects specified in the column header, i.e. N, unless otherwise specified.

[1] Enrolled subjects are all screened subjects who underwent the study device placement procedure, regardless of whether the study device was successfully placed or not.

[2] Safety population will include all enrolled subjects who underwent a successful study device placement procedure.

[3] Screen failure as primary reason for exiting study collected on the study exit status form.

Reference: Listing xxx.

Program Location: \\xx\xxx\xxx\xxx\xxxxxx\xxxxxxxxxxxxxxxx\xxxx\xxxxx.sas

date

time

CONFIDENTIAL

Sebela Pharmaceuticals Development LLC
CMDOC-0022

Page x of y

Table 14.1.2
Subject Disposition by Site (All Enrolled Subjects)

Description	All Subjects (N=xx) n (%)
Site 1 xxx	
Enrolled	n (%)
Discontinued 1-Year Study Prematurely	n (%)
Completed 1-Year Study	n (%)
Entered the Extension Study	n (%)
Discontinued Extension Study Prematurely	n (%)
Completed Extension Study	n (%)
Site 2 xxx	
Enrolled	n (%)
Discontinued 1-Year Study Prematurely	n (%)
Completed 1-Year Study	n (%)
Entered the Extension Study	n (%)
Discontinued Extension Study Prematurely	n (%)
Completed Extension Study	n (%)

Note: Completed the study are subjects who completed 1-Year study but did not entered extension study or who completed extension study.

Note: Subjects who transferred to another site are included only in their initial site.

Note: Subject [REDACTED] transferred to site [REDACTED] subject [REDACTED] transferred to site [REDACTED], subject [REDACTED] transferred to site [REDACTED].

Reference: Listing xxx.

Program Location: \\xx\xxx\xxx\xxx\xxxxxx\xxxxxxxxxxxxxxxx\xxxx\xxxxx.sas date time

Programmer notes: Sort by site ID and repeat for all other sites.

CONFIDENTIAL

Sebela Pharmaceuticals Development LLC
CMDOC-0022

Page x of y

Table 14.1.3
Subjects at Each Scheduled Study Visit (All Enrolled Subjects)

Study Visit	All Subjects (N=xx) n (%)
Visit 1/Screening	n (%)
Visit 2 (Day 1)	n (%)
Visit 3 (Week 6±1)	n (%)
Visit 4 (Week 13±2)	n (%)
Visit 5 (Week 26±2)	n (%)
Visit 6 (Week 52±2)	n (%)
Visit 7 LTFU1	n (%)
Visit 8 LTFU2	n (%)
Visit 9 LTFU3	n (%)
Visit 10 LTFU4	n (%)
Follow Up	
Early Termination	

Note: LTFU1= Month 18, LTFU2= Month 24, LTFU3= Month 30, LTFU4=Month 36.

Note: Follow Up is the CRF collected visit after IUD removal.

LTFU= Long Term Follow up.

Reference: Listing xxx.

Program Location: \\xx\xxx\xxx\xxx\xxxxxx\xxxxxxxxxxxxxxxx\xxxx\xxxxx.sas

date

time

CONFIDENTIAL

Sebela Pharmaceuticals Development LLC
CMDOC-0022

Page x of y

Table 14.1.4
Subjects with Protocol Deviations (All Enrolled Subjects)

Type of Deviation	All Subjects (N=xx)	
	Events n	Subjects n (%)
Number of Events / Subjects with any deviation	n	n (%)
Subject not consented properly	n	n (%)
Scheduled visit completed out of specified window	n	n (%)
Deviation from protocol-defined procedure	n	n (%)
...	n	n (%)
<All categories on source listing>	n	n (%)

Reference: Listing xxx.

Program Location: \\xx\xxx\xxx\xxx\xxxxxx\xxxxxxxxxxxxxxxxxxxx\xxxx\xxxxx.sas

date

time

CONFIDENTIAL

Sebelo Pharmaceuticals Development LLC
CMDOC-0022

Page x of y

Table 14.1.5
Analysis Populations (All Enrolled Subjects)

Description	All Subjects (N=xx) n (%)
Enrolled [1]	n (%)
Safety [2]	n (%)
Evaluable for Pregnancy (EP) [3]	n (%)
Evaluable for Cycle Control (ECYC) [4]	n (%)
Extension[5]	n (%)

[1] Enrolled subjects are all screened subjects who underwent the study device placement procedure, regardless of whether the study device was successfully placed or not.

[2] Safety analysis population will include all enrolled subjects who underwent a successful study device placement procedure.

[3] Evaluable for pregnancy (EP) analysis population will include only those safety subjects who underwent the study device placement successfully, and must meet requirements 1 (between 18 to 35 years of age (inclusive) at enrolment), 2 (at least one report of pregnancy status after being enrolled) and 3 (do not have pre-treatment pregnancy, which is defined as the estimated conception date being before the insertion date) to be EP. Subjects must also meet either requirement 4 (have at least 1 cycle of e-diary with intercourse and without any backup contraception or emergency contraception) or 5 (became pregnant while LevoCept was in place) to be EP.

[4] Evaluable for Cycle Control (ECYC) analysis population will include only those safety subjects with at least one cycle for which: A) a pregnancy did not occur; and B) there is bleeding related e-diary data.

[5] Extension population will include all safety subjects who agree to continue study device use after 12 months, up to 2 additional years for a total maximum of 3 years.

Reference: Listing xxx.

Program Location: \\xx\xxx\xxx\xxx\xxxxxx\xxxxxxxxxxxxxxxx\xxxx\xxxxx.sas

date

time

CONFIDENTIAL

Sebela Pharmaceuticals Development LLC
CMDOC-0022

Page x of y

Table 14.1.6
Demographics and Baseline Characteristics (All Enrolled Subjects)

Characteristic	All Subjects (N=xx)
Age (years)[1]	
n	xx
Mean	xx.x
SD	xx.xx
Median	xx.x
Min	xx
Max	xx
Age Group	
18 - 35	n (%)
36 - 40	n (%)
Ethnicity	
Hispanic or Latino	n (%)
Not Hispanic or Latino	n (%)
Unknown	n (%)
Race[2]	
American Indian or Alaskan Native	n (%)
Asian	n (%)
Black or African American	n (%)
Native Hawaiian or Other Pacific Islander	n (%)
White	n (%)
More than one race	n (%)
Unknown	n (%)

Note: Percentages are based on the number of subjects specified in the column header, i.e. N, unless otherwise specified.

Note: For subjects () without study device successfully placed, baseline weight, height and BMI are defined as last non-missing value on or before the day of later study device placement attempt.

[1] Age (years) = (Date of informed consent - Date of birth) / 365.25, rounded down to the nearest year.

[2] Subjects could mark more than one race.

BMI = Body Mass Index; Max = Maximum; Min = Minimum; SD = Standard Deviation.

Reference: Listing xxx.

Program Location: \\xx\xxx\xxx\xxx\xxxxxx\xxxxxxxxxxxxxxxx\xxxx\xxxxx.sas date time

Programmers note: Table will continue summary statistics for Weight, height, and BMI, as shown for Age.

CONFIDENTIAL

Sebela Pharmaceuticals Development LLC
CMDOC-0022

Page x of y

Table 14.1.6
Demographics and Baseline Characteristics (All Enrolled Subjects)

Programmers note: Continued table

Characteristic	All Subjects (N=xx)
Marital Status	
Married	n (%)
Divorced	n (%)
Separated	n (%)
Single	n (%)
Widowed	n (%)
Parity	
Parous	n (%)
Nulliparous	n (%)
Weight (kg)	
...	
Height (cm)	
...	
BMI (kg/m2)	
...	
BMI Category	
Underweight (<18.5)	n (%)
Normal (18.5-24.9)	n (%)
Overweight (25.0-29.9)	n (%)
Obese (>=30)	n (%)

Note: Percentages are based on the number of subjects specified in the column header, i.e. N, unless otherwise specified.

Note: For subjects [REDACTED] without study device successfully placed, baseline weight, height and BMI are defined as last non-missing value on or before the day of later study device placement attempt.

[1] Age (years) = (Date of informed consent - Date of birth) / 365.25, rounded down to the nearest year.

[2] Subjects could mark more than one race.

BMI = Body Mass Index; Max = Maximum; Min = Minimum; SD = Standard Deviation.

Reference: Listing xxx.

Program Location: \\xx\xxx\xxx\xxx\xxxxxx\xxxxxxxxxxxxxxxx\xxxx\xxxxx.sas date time

Programmers note: Table will continue summary statistics for Weight, height, and BMI, as shown for Age.

CONFIDENTIAL

Sebela Pharmaceuticals Development LLC
CMDOC-0022

Page x of y

Table 14.1.7
Medical History (All Enrolled Subjects)

Body System	All Subjects (N=xx) n (%)
Allergies (including intolerance to nickel and copper)	n (%)
Cardiovascular	n (%)
Gastrointestinal	n (%)
Thyroid	n (%)
HEENT	n (%)
Hematological	n (%)
Hepatobiliary	n (%)
Immunological	n (%)
Integumentary	n (%)
Lymphatic	n (%)
Musculoskeletal	n (%)
Neurological	n (%)
Reproductive/Gynecologic	n (%)
Respiratory	n (%)
Urinary	n (%)
Endocrine	n (%)
Other	n (%)

Note: Subject reporting the same body system multiple times will be counted only once for that body system.

Reference: Listing xxx.

Program Location: \\xx\xxx\xxx\xxx\xxxxxx\xxxxxxxxxxxxxxxx\xxxx\xxxxx.sas

date

time

CONFIDENTIAL

Sebela Pharmaceuticals Development LLC
CMDOC-0022

Page x of y

Table 14.1.8
Gynecological History (All Enrolled Subjects)

Description	All Subjects (N=xx) n (%)
Pain During Intercourse	
No Pain	n (%)
Some Pain	n (%)
Painful	n (%)
Moderately Painful	n (%)
Very Painful	n (%)
Missing	n (%)
Prior Contraception[1]	
Oral Contraception	n (%)
Double Barrier Method	n (%)
Injectable	n (%)
Implantable	n (%)
Condom	n (%)
IUD	n (%)
None	n (%)
Other	n (%)
Currently use Birth Control	
Yes	n (%)
No	n (%)
Current Contraception[1]	
n	n
Oral Contraception	n (%)
Double Barrier Method	n (%)
Injectable	n (%)
Implantable	n (%)
Condom	n (%)
IUD	n (%)
Other	n (%)

Note: Percentages are based on the number of subjects specified in the column header, i.e. N, unless small n is specified for each category.

[1] Subjects could mark more than one contraception method.

[2] Has the subject had any vaginal infections or yeast infections in the past 30 days?

[3] If the subject had any vaginal infections or yeast infections in the past 30 days, were any medications taken for the infection?

[4] If the subject currently breastfeeding, has the subject had two consecutive menses since the last pregnancy?

[5] Is there daily discomfort that can be attributed to gynecological issues (non-menstrual)

CONFIDENTIAL

Reference: Listing xxx.

Program Location: \\xx\xxx\xxx\xxx\xxxxxx\xxxxxxxxxxxxxxxx\xxxx\xxxxx.sas

date

time

CONFIDENTIAL

Sebela Pharmaceuticals Development LLC
CMDOC-0022

Page x of y

Table 14.1.8
Gynecological History (All Enrolled Subjects)

Programmers note:Continued table

Description	All Subjects (N=xx) n (%)
Infections[2]	
Yes	n (%)
No	n (%)
Medications[3]	
n	n
Yes	n (%)
No	n (%)
Ever been Pregnant	
n	n
Yes	n (%)
No	n (%)
Number of Live Births (Natural)	
n	xx
Mean	xx.x
SD	xx.xx
Median	xx.x
Min	xx
Max	xx
Number of Live Births (C-Section)	
n	xx
Mean	xx.x
SD	xx.xx
Median	xx.x
Min	xx
Max	xx

Note: Percentages are based on the number of subjects specified in the column header, i.e. N, unless small n is specified for each category.

[1] Subjects could mark more than one contraception method.

[2] Has the subject had any vaginal infections or yeast infections in the past 30 days?

[3] If the subject had any vaginal infections or yeast infections in the past 30 days, were any medications taken for the infection?

[4] If the subject currently breastfeeding, has the subject had two consecutive menses since the last pregnancy?

[5] Is there daily discomfort that can be attributed to gynecological issues (non-menstrual)

Reference: Listing xxx.

CONFIDENTIAL

Program Location: \\xx\xxx\xxx\xxx\xxxxxx\xxxxxxxxxxxxxxxx\xxxx\xxxxx.sas

date

time

CONFIDENTIAL

Sebela Pharmaceuticals Development LLC
CMDOC-0022

Page x of y

Table 14.1.8
Gynecological History (All Enrolled Subjects)

Programmers note: Continued table

Description	All Subjects (N=xx) n (%)
Currently breastfeeding	
Yes	n (%)
No	n (%)
Two Consecutive Menses[4]	
n	n
Yes	n (%)
No	n (%)
Daily discomfort[5]	
Yes	n (%)
No	n (%)
If Yes, level of this daily discomfort	
n	n
No Pain	n (%)
Some Pain	n (%)
Painful	n (%)
Moderately Painful	n (%)
Very Painful	n (%)

Note: Percentages are based on the number of subjects specified in the column header, i.e. N, unless small n is specified for each category.

[1] Subjects could mark more than one contraception method.

[2] Has the subject had any vaginal infections or yeast infections in the past 30 days?

[3] If the subject had any vaginal infections or yeast infections in the past 30 days, were any medications taken for the infection?

[4] If the subject currently breastfeeding, has the subject had two consecutive menses since the last pregnancy?

[5] Is there daily discomfort that can be attributed to gynecological issues (non-menstrual)

Reference: Listing xxx.

Program Location: \\xx\xxx\xxx\xxx\xxxxxx\xxxxxxxxxxxxxxxx\xxxx\xxxxx.sas

date

time

CONFIDENTIAL

Sebela Pharmaceuticals Development LLC
CMDOC-0022

Page x of y

Table 14.1.9
Menstrual History (All Enrolled Subjects)

Description	All Subjects (N=xx) n (%)
Menstrual Cycle Over The Past 3 Months	
Regular	n (%)
Irregular	n (%)
If Regular, had 3 Consecutive Periods	
n	n
Yes	n (%)
No	n (%)
Frequency	
Less than 25 days	n (%)
25-30 days	n (%)
31-40 days	n (%)
More than 40 days	n (%)
Average length	
Irregular	n (%)
Less than 3 days	n (%)
3-5 days	n (%)
More than 5 days	n (%)
Usual flow	
None	n (%)
Light	n (%)
Moderate	n (%)
Heavy	n (%)
Usual level of discomfort caused by cramping	
None	n (%)
Mild	n (%)
Moderate	n (%)
Severe	n (%)

Note: Percentages are based on the number of subjects specified in the column header, i.e. N, unless small n is specified for each category.
[1] When not using Hormonal Contraception.

Reference: Listing xxx.

Program Location: \\xx\xxx\xxx\xxx\xxxxxx\xxxxxxxxxxxxxxxx\xxxx\xxxxx.sas

date

time

CONFIDENTIAL

Sebela Pharmaceuticals Development LLC
CMDOC-0022

Page x of y

Table 14.1.9
Menstrual History (All Enrolled Subjects)

Programmers note: Continued table

Description	All Subjects (N=xx) n (%)
Spotting between periods	
None	n (%)
Occasionally	n (%)
Regularly	n (%)
Day in current menstrual cycle	
n	xx
Mean	xx.x
SD	xx.xx
Median	xx.x
Min	xx
Max	xx
Used Hormonal Contraception in the Last 3 Months	
Yes	n (%)
No	n (%)
Menstrual Cycles Regular[1]	
n	n
Yes	n (%)
No	n (%)
Frequency[1]	
n	n
Less than 25 days	n (%)
25-30 days	n (%)
31-40 days	n (%)
More than 40 days	n (%)

